5.8.2. Analysis of Adverse Events of Special Interest

Treatment-emergent adverse events of special interest (AESI), as listed in Section 4.8.1.2, will be presented by SOC and PT as applicable. AESI are defined by SMQ, CMQ, lab data, and/or dedicated e-CRF as described in [Appendix 10.3](#).

For Group B, the following variables will also be tabulated for infusion reactions TEAEs:

- Intensity of the event (mild, moderate, or severe);
- Number of events divided by the number of study treatment administrations received in respective treatment periods;

- Time from first study treatment administration (DBTP or OLTP depending on the analysis) to first infusion reaction;

For Group A, the following variables will also be tabulated for injection reactions TEAEs:

- Intensity of the event (mild, moderate, or severe);
- Number of events divided by the number of study treatment administrations received in DBTP treatment period;
- Time from first study treatment administration to first injection reaction;
- Description of the highest intensity of each symptom recorded in the specific e-CRF page with table and bar chart.

5.8.3. Clinical Laboratory Measurements

The following definitions will be applied to laboratory parameters:

- Double-blind treatment period: The treatment period used for quantitative analysis in the double-blind period is defined as the day after the first study drug administration to the day of the last double-blind study drug injection + 7 days for Group A. For Group B, the treatment period is defined from the day after the first administration of double-blind study treatment to the day of the last administration of double-blind study treatment + 28 days for those patients not proceeding into the open-label treatment period, or up to the day of the first open-label study treatment administration for those patients proceeding into the open-label treatment period.
- Open-label treatment period: The treatment period used for quantitative analysis in the open-label study period is defined from the day after the first dose of open-label study treatment to the day of the last dose of open label study treatment + 28 days.

For respective treatment period (DBTP and OLTP), clinical laboratory parameter actual values (quantitative) and change from baseline values will be descriptively summarized at baseline and each post-baseline visit by at least patient number, mean, median, Q1, Q3, SD, minimum and maximum. Clinical laboratory parameters mean changes from baseline, with the corresponding SE, can be plotted at each visit in the case results warrant further investigation. These parameters will be presented by the biological functions defined in Section 4.8.2. For glucose, only fasting samples will be included in the summaries.

Individual patient laboratory parameter measurements will be additionally evaluated by PCSV criteria (See Appendix 10.4), specifically identifying patients with at least one post-baseline measurement that meets the PCSV criteria within the respective TEAE periods. These laboratory parameters will be presented by the biological functions defined in Section 4.8.2. The incidence of PCSVs at any time during the respective TEAE periods will be summarized regardless of the baseline level, and again according to the following baseline categories:

- Normal (according to PCSV criterion/criteria)/missing
- Abnormal according to PCSV criterion or criteria

Patient listings of laboratory measurements that meet PCSV criteria will be provided for the report appendix. For those laboratory parameters that don't have an associated PCSV criteria,

similar summary tables can be provided based on measurements outside the central laboratory normal ranges, if applicable.

Drug-induced liver injury

For respective treatment period (DBTP and OLTP), an evaluation of drug-induced serious hepatotoxicity (eDISH) with the graph of distribution of peak values of ALT versus peak values of total bilirubin will also be presented using post-baseline values during respective TEAE periods. Note that the ALT and total bilirubin values are presented on a logarithmic scale. The graph will be divided into 4 quadrants with a vertical line corresponding to 3 x ULN for ALT and a horizontal line corresponding to 2 x ULN for total bilirubin.

Patient listing of possible Hy's law cases identified by treatment group (i.e., patients with any elevated ALT > 3 x ULN, and associated with an increase in bilirubin > 2 x ULN, concomitantly or not) with ALT, AST, ALP, total bilirubin, and if available direct and indirect bilirubin will be provided.

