7.6. Method of Treatment Assignment

Patients will be randomized within either Group A (SC treatment regimens) in a 1:1:1:1 ratio or Group B (IV treatment regimens) in a 1:1:1 ratio. Enrollment of IV cohorts will occur before enrollment of SC cohorts; accordingly, enrollment of Group A will not begin until Group B enrollment is completed. There will be 144 patients randomized to Group A (36 patients per treatment group), with 108 patients exposed to SC evinacumab and 36 exposed to SC placebo. There will be 108 patients randomized to Group B (36 patients per treatment group), with 72 patients exposed to IV evinacumab and 36 exposed to IV placebo.

Patients in Group A will receive treatment from day 1 through week 16 (last dose of study drug at week 15). Patients in Group B will receive treatment from day 1 through week 24 (last dose of study drug week 20). Patients will be randomized to a treatment group according to a central randomization scheme provided by an interactive voice response system (IVRS)/interactive web response system (IWRS) to the designated study pharmacist (or qualified designee).

Randomization will be stratified by study treatment route of administration (Group A or B), high-intensity statin (Yes/No), and HeFH (Yes/No) at baseline. High-intensity statin is defined as rosuvastatin 20 mg or 40 mg daily, atorvastatin 40 mg or 80 mg daily, or simvastatin 80 mg daily (if already on this dose for >1 year). To ensure that an adequate number of patients with HeFH are included, randomization will be stratified 2:1 (HeFH:non-HeFH; 24:12) within each treatment group.

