10.4.4.2. Other Safety

Definitions

The following definitions will be applied to laboratory parameters and vital signs:

- The potentially clinically significant value (PCSV) criteria are defined as abnormal values considered medically important by the sponsor according to predefined criteria/thresholds based on literature review and defined by the sponsor for clinical laboratory tests and vital signs. PCSV criteria will be provided in the SAP.
- PCSV criteria will determine which patients had at least 1 PCSV during the respective TEAE periods (double-blind or open-label), taking into account all evaluations performed during the respective TEAE periods, including unscheduled or repeated evaluations. The number of all such patients will be the numerator for the PCSV percentage.
- Double-blind treatment period: The treatment period used for quantitative analysis in the double-blind period is defined as the day after the first study drug administration to the day of the last double-blind study drug injection + 7 days for Group A. For Group B, the treatment period is defined from the day after the first administration of double-blind study treatment to the day of the last administration of double-blind study

treatment + 28 days for those patients not proceeding into the open-label treatment period, or up to the day of the first open-label study treatment administration for those patients proceeding into the open-label treatment period.

- Open-label treatment period: The treatment period used for quantitative analysis in the open-label study period is defined from the day after the first dose of open-label study treatment to the day of the last dose of open label study treatment + 28 days.

Analysis

Summary statistics of all laboratory variables (including lipid HDL-C) and all vital signs parameters (raw data and changes from baseline) will be calculated for each protocol scheduled visit assessed during the respective treatment periods. For selected parameters, mean changes from baseline with the corresponding standard error will be plotted over time (at same time points) in each treatment group.

The incidence of PCSVs at any time during the respective TEAE periods will be summarized regardless of the baseline level, and again according to the following baseline categories:

- Normal/missing
- Abnormal according to PCSA criterion or criteria

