3.1.2. Modified Intent-to-Treat (mITT)

The modified ITT (mITT) population is defined as the all randomized population who took at least 1 dose or part of a dose of study drug and have an evaluable primary endpoint. The endpoint is considered evaluable when both of the following conditions are met:

- Availability of at least 1 measurement value for calculated LDL-C before first dose of study drug (i.e., baseline).
- Availability of at least 1 calculated LDL-C value during the efficacy treatment period and within one of the efficacy analysis windows in the DBTP up to week 16. The group A (SC dose regimens) efficacy treatment period is defined as the time from the first study drug administration up to 14 days after the last double-blind study drug injection. The Group B (IV dose regimens) efficacy treatment period is defined as the time from the first study drug administration up to 35 days after the last double-blind study drug infusion, or up to the first dose of the open-label study drug, whichever is earlier.

Patients in the mITT population will be analyzed according to the treatment group allocated by randomization.

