5.9. Analysis of Other Variables

In general, for the double-blind period, the summary of results for other variables for patients in the double-blind SAF population will be presented by route of administration (Group A or Group B) and pooling the evinacumab dose regimens within each route of administration (Group A or Group B), with the intent to maximize efforts to identify potential safety signals. The treatment group data (individual evinacumab dose regimens and placebo) will also be presented with the intent to support the pooled dose regimens. No formal inferential testing will be performed. Summaries will be descriptive in nature.

For Group B, summaries of safety results for the open-label period will be presented for patients in the open-label SAF, by the total number of patients administered open-label study treatment (ie., 15 mg/kg IV), as well as by the patient subgroups of study treatment received in the DBTP (ie., 5 mg/kg IV, 15 mg/kg IV, or placebo). No formal inferential testing will be performed for either period. Summaries will be descriptive in nature.

All measurements, scheduled or unscheduled, fasting or not fasting, will be assigned to Global Analysis Windows ([Appendix 10.2](#)) in order to provide an assessment for all post-baseline visit.

Hs-CRP, HbA1c, and HDL-C parameters will be summarized for the number of patients with data, mean, SD, median, minimum, maximum, Q1 and Q3 by analysis visit during the treatment period. The medians (with Q1-Q3) will be plotted for hs-CRP. The means (+/-SE) will be plotted for HbA1c and HDL-C. In addition, HbA1C will be summarized at each visit by diabetic status as recorded in the medical history e-CRF page (regardless of the ongoing status). Applying the

PCSV criteria to HbA1c at any time during the TEAE period, the number of patients (and percentages) meeting the criteria will be summarized.

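### By-visit laboratory, vital-sign and HbA1c summaries close exactly on the nominal end-of-treatment day, so visits that are on time within ±3 days can be left out

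*SAP*

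**What the plan says.** SAP 5.8.3 (laboratory) and 5.8.4 (vital signs) define the period for quantitative analysis in the same words, as does Protocol 10.4.4.2.

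- **Group A:** the period runs "to the day of the last double-blind study drug injection + 7 days for Group A".
- **Group B, double-blind, not continuing:** it runs to the last "treatment + 28 days for those patients not proceeding into the open-label treatment period".
- **Group B, double-blind, continuing:** it runs instead "or up to the day of the first open-label study treatment administration for those patients proceeding into the open-label treatment period".
- **Open label:** it runs "to the day of the last dose of open label study treatment + 28 days".

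Protocol 10.4.4.2 makes this period a filter: summary statistics "will be calculated for each protocol scheduled visit assessed during the respective treatment periods". SAP 5.9 summarizes HbA1c, hs-CRP and HDL-C "by analysis visit during the treatment period".

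For on-treatment efficacy, SAP 3.1.2 sets a longer period: "up to 14 days after the last double-blind study drug injection" for Group A, and 35 days after the last infusion for Group B, again cut at the first open-label dose.

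**The concern.** The interval after the last dose equals one dosing interval with nothing added, whereas the injection day and the visit day can each move by 3 days. A visit that fully complies with the schedule can therefore fall outside the period and drop out of the by-visit tables. Whether it drops out depends only on how the visit date fell relative to the last dose.

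Group A has most to lose. Protocol Table 3 schedules HbA1c once in the double-blind period, at week 16, so an excluded visit removes that patient's only scheduled on-treatment HbA1c value from the summary. Week 16 is also the longest-exposure point for chemistry, haematology and vital signs in that group, as week 72 is for the open-label period. There is an inconsistency within one visit too: with a last injection on day 106, LDL-C from a day-115 visit counts as on-treatment under SAP 3.1.2, while chemistry, vital signs and HbA1c from the same visit do not.

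**Working it through.** **Inputs**

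- Group A: "last dose of study drug at week 15" (Protocol 7.6), which is day 106. The week-16 visit is day 113 ±3 (Protocol Table 3). The SC dose window is ±3 days (Protocol 7.1).
- Group B double-blind: last infusion at week 20, day 141. The week-24 visit is day 169 ±3 (Table 4).
- Group B open label: last infusion at week 68, day 477. The week-72 visit is day 505 ±3 (Table 5).
- For IV dose days I used the ±3-day visit window of the schedule. Protocol 7.1 states a wider ±14 days for infusions; I did not use it.

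**Step 1: reproduce the nominal days.** 106 + 7 = 113, 141 + 28 = 169 and 477 + 28 = 505. These are the end-of-treatment days in the study flow diagram (Protocol Figure 1), so the cut falls exactly on the nominal visit.

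**Step 2: last dose on its nominal day.** The visits excluded although on time are days 114–116 (Group A), 170–172 (IV non-continuers) and 506–508 (open label). That is 3 of the 7 permitted days in each case.

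**Step 3: last dose early.** With the last injection on day 105 the cut is day 112, so a visit exactly on day 113 is out. With the last injection on day 103 the cut is day 110, so days 111–116 are out, 6 of 7.

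**Step 4: all in-window combinations.** Let d and v be the day offsets of the last dose and the visit, each from −3 to +3. A visit is excluded when v > d. Of 7 × 7 = 49 pairs, 7 are ties and the other 42 split evenly, giving 21 of 49 = 42.9%.

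**Step 5: other timing assumptions.** The documents give no timing data, so the share is a range. Dose and visit offsets are taken as independent except in the first row.

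| Assumed timing | Share excluded | Per arm of 36 |
|---|---|---|
| Visit exactly one dosing interval after last dose | 0% | 0 |
| 80% exact, 10% at each of ±1 day | 0.1 × 0.9 + 0.8 × 0.1 = 17% | 36 × 0.17 = 6.1 |
| Triangular over ±3 days (weights 1, 2, 3, 4, 3, 2, 1) | 41% | 36 × 0.414 = 14.9 |
| Uniform over ±3 days | 43% | 36 × 0.429 = 15.4 |

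The last column assumes that all 36 patients in an arm receive the last scheduled dose and attend the visit.

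**Step 6: with added tolerance.** The largest possible v − d is 3 − (−3) = 6. Adding 7 days (+14 SC, +35 IV) therefore excludes 0 of 49. Adding only 3 days (+10, +31) still excludes pairs with v − d of 4, 5 or 6, which is 3 + 2 + 1 = 6 of 49 (12%).

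**The case against.** The best counter-argument is that the SAP may not drop these values at all. SAP 5.8 and 5.9 assign all measurements to the Global Analysis Windows, SAP 6.4 applies the windows to all analyses, and the Group A week-16 window runs from day 110 to day 140. SAP 5.9 also refers to the treatment period without pointing back to 5.8.3. This shows that the text is open to two readings. It does not remove the problem: the windows label a value with a visit, nothing says they override the treatment-period limit, and Protocol 10.4.4.2 applies that limit expressly.

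A second argument is that +7 and +28 days match the exposure-duration formulas in SAP 4.6. That is true, but SAP 3.1.2 already separates an on-treatment period from exposure. A smaller fix would be to count the scheduled end-of-treatment visit whenever it falls in its analysis window. That works, but for Group A it admits values up to 140 − 106 = 34 days after the last injection.

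The objections on scope stand in full. A reader might infer any of the following, and the documents do not support them:

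- **That ECG findings or safety signals are lost.** SAP 5.8.5 repeats the period definition, but its ECG abnormality and PCSV counts use the TEAE period, as do laboratory and vital-sign PCSVs, eDISH, adverse events and the HbA1c criterion for new-onset diabetes. For patients not entering open label, and for the open-label period, the TEAE period runs to 168 days after the last dose.
- **That IV week-24 values are generally at risk.** Patients entering open label keep them.
- **That open-label patients lose their only HbA1c.** It is also drawn at weeks 36, 48 and 60.
- **That 43% is the expected loss.** It rests on independent, uniform timing. Patients who keep the same weekday lose nothing.

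**Conclusion.** The point holds for the by-visit descriptive summaries of laboratory tests, vital signs, HbA1c, hs-CRP and HDL-C, at three places: week 16 in Group A, week 72 in open label, and week 24 for IV patients who do not continue. The day arithmetic is certain. The size is not: between 0% and 43% of on-time end-of-treatment visits under the timing assumptions shown, with 17% under a tight one. The conclusion also rests on reading the treatment period as a filter, which Protocol 10.4.4.2 supports and the SAP does not contradict.

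The summaries are descriptive, with no formal safety testing, and no efficacy result changes. The matter is still worth correcting because it bears on the only scheduled on-treatment HbA1c in Group A and because two programmers could implement the present text differently.

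**What to change.** In SAP 5.8.3 and 5.8.4 and Protocol 10.4.4.2, end the quantitative period at last injection + 14 days for Group A, and at last infusion + 35 days for Group B patients who do not continue and for the open-label period, matching SAP 3.1.2. State in SAP 5.9 that the same period applies. Keep the cut at the first open-label dose for patients who continue. The ECG counts in SAP 5.8.5 need no change.

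The cost is a wording change and one derivation. The downside is that a few descriptive values up to 7 days further from the last dose are included, a tolerance the SAP already accepts for efficacy. The guarantee of no exclusions covers patients whose last scheduled dose was given within ±3 days. After a skipped final injection, or an infusion given much earlier within the ±14 days of Protocol 7.1, an end-of-treatment visit could still fall outside.

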 - Investigator or any sub-investigator, pharmacist, study coordinator, other study staff or relative thereof directly involved in the conduct of the protocol, etc.
 - Presence of any other conditions (eg, geographic or social), either actual or anticipated, that the investigator feels would restrict or limit the patient's participation for the duration of the study
12. Laboratory findings during screening period (not including randomization labs):
- Triglycerides >400 mg/dL (>4.52 mmol/L) for patients without a known history of diabetes mellitus (1 repeat lab is allowed);
OR
Triglycerides >300 mg/dL (>3.39 mmol/L) for patients with a known history of diabetes mellitus (1 repeat lab is allowed)
 - Positive test for Hepatitis B surface antigen and/or Hepatitis C antibody (associated with a positive HCV ribonucleic acid [RNA] polymerase chain reaction)
 - Positive serum beta-human chorionic gonadotropin or urine pregnancy test in women of childbearing potential
 - Estimated glomerular filtration rate <30 mL/min/1.73 m² according to 4-variable MDRD study equation (calculated by central lab)
 - TSH >1.5 x upper limit of normal (ULN) (1 repeat lab is allowed) for patients not on thyroid replacement therapy
 - Alanine aminotransferase (ALT) or aspartate aminotransferase (AST) > 2 x ULN at screening (1 repeat lab is allowed)
 - Creatine phosphokinase (CPK) > 3 x ULN at screening (1 repeat lab is allowed)
13. Systolic blood pressure > 160 mmHg or diastolic blood pressure > 100 mmHg at the screening visit or time of randomization (1 repeat allowed)
14. History of heart failure (New York Heart Association [NYHA] Class III-IV) within 12 months before screening

15. History of MI, unstable angina leading to hospitalization, CABG surgery, PCI, uncontrolled cardiac arrhythmia, carotid surgery or stenting, stroke, TIA, carotid revascularization, endovascular procedure or surgical intervention for peripheral vascular disease within 3 months prior screening
16. Having received LDL apheresis within 2 months before screening
17. Evidence of clinically significant intestinal malabsorption, or a history of ileal bypass, gastric bypass, or other bariatric surgery within 12 months before screening
18. Unstable weight (variation > 5 kg) within 2 months prior to screening visit

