9.4.3. Other Events that Require Accelerated Reporting to Sponsor

The following events also require reporting to the sponsor (or designee) within 24 hours of learning of the event:

Symptomatic Overdose of Study Drug: Accidental or intentional overdose of at least 2 times the intended dose of study drug within the intended therapeutic window, if associated with an AE

Pregnancy: Although pregnancy is not considered an AE, it is the responsibility of the investigator to report to the sponsor (or designee), within 24 hours of identification,

any pregnancy occurring in a female or female partner of a male, during the study or within 24 weeks of the last dose of study drug. Any complication of pregnancy affecting a female study patient or female partner of a male study patient, and/or fetus and/or newborn that meets the SAE criteria must be reported as an SAE. Outcome for all pregnancies should be reported to the sponsor

Adverse Events of Special Interest: All AESIs, serious and non-serious, must be reported within 24 hours of identification using the same reporting process as for SAE reporting, per Section 9.4.2.

Adverse events of special interest for evinacumab include the following:

- Anaphylactic reactions
- Allergic reactions and/or local injection site reactions that require medical treatment or consultation with another physician for further evaluation
- Increase in ALT or AST: ≥ 3 x ULN (if baseline < ULN), or ≥ 2 x baseline value (if baseline \geq ULN)
- Pregnancy
- Symptomatic overdose with IMP
- Neurocognitive events
- New onset of diabetes
- Pancreatitis

Adverse events of special interest for alirocumab include the following:

- Increase in ALT: ALT ≥ 3 x ULN (if baseline ALT < ULN), or ALT ≥ 2 x baseline value (if baseline ALT \geq ULN)
- Allergic events and/or local injection site reactions that require consultation with another physician for further evaluation
- Pregnancy
- Symptomatic overdose with IMP
- Neurologic events that require additional examinations/procedures and/or referral to a specialist
- Neurocognitive events
- Cataracts
- New onset of diabetes:

The definition of new onset of diabetes will be the following:

- Type 1 or type 2 diabetes treatment-emergent adverse event (TEAE) (grouping of MedDRA terms will be specified in the SAP)

and/or

- at least 2 values of HbA1c $\geq 6.5\%$ during the TEAE period

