10.4. Criteria for Potentially Clinically Significant Values (PCSV)

Parameter	PCSV
Clinical chemistry	
ALT	By distribution analysis: >2 ULN and baseline \leq 2 ULN >3 ULN and baseline \leq 3 ULN >5 ULN and baseline \leq 5 ULN >10 ULN and baseline \leq 10 ULN >20 ULN and baseline \leq 20 ULN
AST	By distribution analysis: >2 ULN and baseline \leq 2 ULN >3 ULN and baseline \leq 3 ULN >5 ULN and baseline \leq 5 ULN >10 ULN and baseline \leq 10 ULN >20 ULN and baseline \leq 20 ULN
Alkaline Phosphatase	> 1.5 ULN and baseline \leq 1.5 ULN
Total Bilirubin	> 1.5 ULN and baseline \leq 1.5 ULN > 2 ULN and baseline \leq 2 ULN
Conjugated bilirubin	> 35% total bilirubin (when total bilirubin >1.5 ULN)
ALT and Total Bilirubin	ALT > 3 ULN and Total Bilirubin > 2 ULN and baseline ALT \leq 3 ULN or Total bilirubin \leq 2 ULN
CPK	> 3 ULN and \leq 5 ULN and baseline \leq 3ULN >5 ULN and \leq 10 ULN and baseline \leq 5 ULN >10 ULN and baseline \leq 10 ULN
Creatinine	\geq 150 μ mol/L (adults) \geq 30% from baseline \geq 100% from baseline
CLcr (mL/min) (Estimated creatinine clearance based on the Cockcroft-Gault equation)	\geq 15 - <30 (severe decrease in GFR) \geq 30 - < 60 (moderate decrease in GFR) \geq 60 - <90 (mild decrease in GFR) \geq 90 (normal GFR)
eGFR (mL/min/1.73m ²) (Estimate of GFR based on an MDRD equation)	\geq 15 - <30 (severe decrease in GFR) \geq 30 - < 60 (moderate decrease in GFR) \geq 60 - <90 (mild decrease in GFR) \geq 90 (normal GFR)

Parameter	PCSV
Uric Acid Hyperuricemia: Hypouricemia:	>408 µmol/L <120 µmol/L
Blood Urea Nitrogen	≥17 mmol/L
Chloride	<80 mmol/L >115 mmol/L
Sodium	≤129 mmol/L ≥ 160 mmol/L
Potassium	< 3 mmol/L ≥ 5.5 mmol/L
Glucose Hypoglycaemia Hyperglycaemia	≤ 3.9 mmol/L and < LLN ≥ 7 mmol/L (fasted); ≥ 11.1 mmol/L (unfasted)
HbA1c	>8%
Albumin	≤25 g/L
CRP	> 2 ULN or >10 mg/L, if ULN not provided
Hematology	
WBC	< 3.0 Giga/L (3000/ mm ³) (Non-Black) < 2.0 Giga/L (2000/ mm ³) (Black) ≥16.0 Giga/L (16000/ mm ³)
Lymphocytes	>4.0 Giga/L
Neutrophils	< 1.5 Giga/L (1500/ mm ³) (Non-Black) < 1.0 Giga/L (1000/ mm ³) (Black)
Monocytes	>0.7 Giga/L
Eosinophils	> 0.5 Giga/L (500/ mm ³) or > ULN if ULN ≥ 0.5 Giga/L
Hemoglobin	≤115 g/L (Male); ≤95 g/L (Female) ≥185 g/L (Male); ≥165 g/L (Female) Decrease from Baseline ≥15 g/L Decrease from Baseline ≥20 g/L
Hematocrit	≤0.37 v/v (Male) ; ≤0.32 v/v (Female) ≥0.55 v/v (Male) ; ≥0.5 v/v (Female)
RBC	≥6 Tera/L

Parameter	PCSV
Platelets	< 100 Giga/L (100 000/mm ³) ≥700 Giga/L (700000/mm ³)
Urinalysis	

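### The SAP's possible Hy's law screen has no AST trigger, and no SAP output derives the protocol's baseline-dependent ALT/AST event of special interest

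*SAP*

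**What the plan says.** **Liver-injury screen.** Under drug-induced liver injury, SAP 5.8.3 plans an eDISH plot of peak ALT against peak total bilirubin, with "a vertical line corresponding to 3 x ULN for ALT and a horizontal line corresponding to 2 x ULN for total bilirubin". It also plans a listing of possible Hy's law cases, selected as "patients with any elevated ALT > 3 x ULN, and associated with an increase in bilirubin > 2 x ULN, concomitantly or not". AST is printed in that listing, but only for patients already selected on ALT. The one combined enzyme-and-bilirubin PCSV row in SAP 10.4 is "ALT > 3 ULN and Total Bilirubin > 2 ULN", with a baseline condition. No AST counterpart exists.

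**Single-enzyme bands.** SAP 10.4 gives ALT and AST the same five rows, starting "By distribution analysis: >2 ULN and baseline" at or below that cut-off, then >3, >5, >10 and >20 ULN. SAP 5.8.3 provides patient listings of all laboratory values that meet a PCSV criterion.

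**Hepatic event of special interest (AESI).** For evinacumab, protocol 9.4.3 names "Increase in ALT or AST": at least 3 x ULN if baseline is below ULN, or at least 2 x baseline if baseline is at or above ULN, reportable within 24 hours. The parallel alirocumab item is restricted to one enzyme ("Increase in ALT: ALT"). SAP 4.8.1.2 and 10.3 identify hepatic disorders without an e-CRF tick box, from an SMQ, the PCSV criteria and the eDISH plot. SAP 1.2.3 lists four modifications from the protocol, and none concerns this.

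**Eligible baselines.** Protocol 6.2.3 excludes "Alanine aminotransferase (ALT) or aspartate aminotransferase (AST) > 2 x ULN at screening", with one repeat allowed, so patients with enzymes between 1 and 2 x ULN can enter.

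**The concern.** For the investigational drug the protocol treats an AST rise as a signal in its own right, and it contrasts this with an ALT-only item for alirocumab. The SAP's combined liver screen does not carry this through. If AST rises with bilirubin while ALT stays at or below 3 x ULN, no planned output puts the two findings together for that patient. Someone would have to notice the same patient in two separate listings.

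The second issue is reconciliation. Sites are told to report events by a rule that depends on baseline, and the SAP tabulates hepatic events by rules that do not. The reported AESIs and the tabulated ones will then differ, with nothing in the SAP to explain why. The same appendix carries over the protocol's HbA1c and fasting-glucose rules for new-onset diabetes in detail, so deriving a laboratory AESI from the protocol is already the SAP's practice.

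Long-term safety is a stated purpose of Group B (protocol 3.2.1), and the first-step analysis may go to health authorities (SAP 7.1).

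**Working it through.** The documents state no figure on this point, so there is nothing to reproduce. The check is a logical cross-classification of the two rules for one enzyme. Let b be the baseline and p the peak, both in multiples of ULN.

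**Rules**
- Protocol 9.4.3: qualifies if p ≥ 3 when b < 1, or p ≥ 2b when b ≥ 1.
- SAP 10.4: in band k if p > k and b ≤ k, for k = 2, 3, 5, 10, 20.

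**Step 1: does a qualifying value fall in at least one band?**
- b < 1: p ≥ 3 > 2, so band 2 holds.
- 1 ≤ b ≤ 2: p ≥ 2b ≥ 2, so band 2 holds except at exactly b = 1.0, p = 2.0 (the protocol uses ≥, the SAP >).
- 2 < b ≤ 3: p > 4, so band 3 holds. For 3 < b ≤ 5, p > 6, so band 5 holds. For 5 < b ≤ 10, p > 10, so band 10 holds.

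The equality point is the only exception. A grid in steps of 0.05 (b from 0.2 to 2.0, p from 0.2 to 25) agrees: 1 of 16,317 qualifying cells lies in no band.

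**Step 2: can the bands return the protocol count?** For b ≤ 2 every baseline condition is met, so membership of each band depends on p alone. The protocol threshold depends on b: it is 3 below b = 1, then runs from 2 at b = 1 to 4 at b = 2. Two patients with the same p can be in identical bands and differ on the protocol rule:

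| Baseline | Peak | Protocol threshold | Protocol AESI | SAP bands |
|---|---|---|---|---|
| 1.2 | 2.5 | 2 × 1.2 = 2.4 | Yes | >2 only |
| 0.8 | 2.5 | 3.0 | No | >2 only |
| 0.8 | 3.0 | 3.0 | Yes | >2 only |
| 1.8 | 3.2 | 2 × 1.8 = 3.6 | No | >2, >3 |
| 2.0 | 4.0 | 2 × 2.0 = 4.0 | Yes | >2, >3 |

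The first two rows settle it: no band, alone or combined, separates them. On the same grid, 137 qualifying cells lie outside the >3 band. Conversely, 704 non-qualifying cells lie in the >2 band and 100 in the >3 band. These are counts of grid cells, not of patients.

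**Step 3: the liver screen.** Take AST > 3, ALT ≤ 3 and bilirubin > 2 (all x ULN).
- Possible Hy's law listing: not selected, because ALT fails.
- eDISH plot: outside the upper-right quadrant, because ALT is the horizontal axis.
- Combined PCSV row: not met, because ALT fails.
- Single AST and bilirubin PCSV rows: each met, if the baselines are at or below those cut-offs. The patient is then listed twice, unconnected.

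**The case against.** The strongest case against has four parts.

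1. *Nothing goes unlisted.* A reader might infer that qualifying hepatic cases disappear, or that a value of exactly 3.0 x ULN is not a PCSV. The documents do not support either. The >2 ULN rows apply to both enzymes, 3.0 exceeds 2, and all PCSV values are listed by patient. This part stands: only the combined flag and the protocol-rule count are missing.

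2. *The ALT-only Hy's law rule breaks no protocol definition.* A reader might take it as a protocol departure. It is not, because the protocol contains no Hy's law or eDISH specification. The SAP screen is also broad in time, since it does not require the two rises to coincide. This stands, so the point on the screen is a weakness of the analysis and not an inconsistency.

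3. *Protocol 9.4.3 governs site reporting, not tabulation.* Protocol 10.4.4.1 defines events of interest by preferred term or a grouping of terms, and 10.4.4.2 leaves PCSV criteria to the SAP. The SAP also uses an SMQ, so the bands are not the sole replacement. This stands in part. The SAP was free to choose its outputs, but it presents hepatic disorders as an AESI, does not apply the protocol's only definition of that AESI and does not say so. The SMQ's term list is not in the documents, so its coverage cannot be judged.

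4. *AST also rises from muscle, and most patients take statins.* This is a real trade-off. CPK is in the same chemistry panel (protocol 8.2.3.4), so such cases can be recognised.

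**Conclusion.** The point holds as a gap in flagging and counting. The plan has no output that flags an AST-driven rise accompanied by bilirubin above 2 x ULN. It also has none that counts the hepatic AESI by the protocol's rule, and this change is undeclared.

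Its size is limited. Apart from one equality point, every qualifying ALT or AST value with a known baseline up to 10 x ULN reaches a PCSV listing. Safety summaries are descriptive (SAP 5.8), and efficacy, alpha and sample size are untouched. The documents give no event rates, so the number of affected patients cannot be stated and may be zero.

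The conclusion rests on reading the SAP rules literally and on treating each enzyme separately. It is a worthwhile, inexpensive improvement, not a defect that threatens the trial's conclusions.

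**What to change.** - In SAP 5.8.3 and 10.4, make the possible Hy's law listing and the combined PCSV row trigger on ALT or AST above 3 x ULN with total bilirubin above 2 x ULN. Apply the row's baseline condition to whichever enzyme triggers.
- Add an AST version of the eDISH plot beside the ALT one.
- In the hepatic row of SAP 10.3, add a derived flag for the protocol 9.4.3 ALT/AST rule, using at-least inequalities as the protocol does. Keep the SMQ and the bands as they are.
- If the sponsor prefers not to derive the flag, state the change in SAP 1.2.3 so that the difference from the reported AESIs is explained.

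The cost is SAP wording and programming. ALT, AST, bilirubin and CPK are already in the chemistry panel, so no new data are needed. The downside is that a few muscle-related AST rises will be listed; showing CPK next to them lets a reader set them aside.
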